5.6 Follow-up Assessments

5.6.1 Safety Follow-up (30 Days Post Last Dose)

Patients must have a safety evaluation 30 days after the last dose of study drug. The following assessments will be performed:

- Assess for AEs
 - Ongoing AEs must be followed clinically until the event is resolved, deemed stable, or the patient starts another treatment for their disease
- Record only those medications (prescription, nonprescription, and nutritional supplements) administered in conjunction with an AE, as well

as any antineoplastic therapies initiated since discontinuation of study drug.

5.6.2 Long-term Follow-up (Starting 30 Days Post End of Study out to 2 Years)

Additionally, all study patients will be attempted to be contacted by phone, if possible, every 6 months to assess for date of death, date of stem cell transplant, date of relapse, or continued remission beginning the month after the patient completes the End of Study assessments to 24 months after Day of First Dose regardless of how many cycles a patient receives. When telephone contact is not possible, medical records will serve as the surrogate to assess for these outcomes.

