7.10.5. Neutrophil Recovery

Time to neutrophil recovery is defined for all patients and is measured from the date of first dose (Day 1) until the first day the absolute neutrophil count (ANC) is $\geq 1 \times 10^9 / L$ for 14 consecutive days. It is assumed that the ANC remains above the threshold value of $1 \times 10^9 / L$ unless there is evidence that it did not. Therefore, a patient with ANC $\geq 1 \times 10^9 / L$ on Day 45 and without another assessment for > 14 days will have a time to neutrophil recovery of 45 days.

Rules for censoring time to neutrophil recovery are:

- A patient with ANC <1x10⁹/L as of the date he is lost to follow-up will have his time to neutrophil recovery censored on the date of his last assessment of any type
- A patient with ANC <1x10⁹/L as of the database lock will have his time to neutrophil recovery censored on the date of his last assessment of any type

Summary statistics will include the number and percentage of censored times to neutrophil recovery, quartile times to neutrophil recovery, 95% Cls for the quartile times to neutrophil recovery, and KM "survival" percentages with 95% Cls at select milestone times (e.g., 42, 49 and 56 days).

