7.10.6. Platelet Recovery

Time to platelet recovery is defined for all patients and is measured from the date of first dose (Day 1) until the first day the platelet count is $\geq 100 \times 10^9 / L$ for 14 consecutive days. It is assumed that the platelet count remains above the threshold value of $100 \times 10^9 / L$ unless there is evidence that it did not. Therefore, a patient with platelet $\geq 100 \times 10^9 / L$ on Day 60 and without another assessment for >14 days will have a time to platelet recovery of 60 days.

Rules for censoring time to platelet recovery are:

- A patient with platelet count <100x10⁹/L as of the date he is lost to follow-up will
 have his time to platelet recovery censored on the date of his last assessment of
 any type
- A patient with platelet count <100x10⁹/L as of the database lock will have his time to platelet recovery censored on the date of his last assessment of any type

Summary statistics will include the number and percentage of censored times to platelet recovery, quartile times to platelet recovery, 95% CIs for the quartile times to platelet recovery, and KM "survival" percentages with 95% CIs at select milestone times (e.g., 49, 56 and 63 days).

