Appendix 2. Sample Table Template

Tolero Pharmaceuticals ALV-101

Patient Disposition (Intent-to-Treat Population) Table X.X

Page 1 of 327

	Alvocidib $20/30 \text{ mg/m}^2$ $(N=3)$	Alvocidib $30/40 \text{ mg/m}^2$ (N=3)	Alvocidib $30/50 \text{ mg/m}^2$ $(N=3)$	Alvocidib $30/60 \text{ mg/m}^2$ $(N=13)$	Study Total (N=22)
Study Center Columbia University Medical Center University of North Carolina Johns Hopkins University	3 (100%)	1 (33.3%) 2 (66.7%) 0	3 (100%) 0	2 (15.4%) 7 (53.8%) 4 (30.8%)	6 (27.3%) 12 (54.5%) 4 (18.2%)
Country United States	3 (100%)	3 (100%)	3 (100%)	13 (100%)	22 (100%)
Protocol Version Amendment 2 Amendment 3 Amendment 4	1 (33.3%) 2 (66.7%) 0	3 (100%) 0	3 (100%) 0	0 0 13 (100%)	1 (4.5%) 8 (36.4%) 13 (59.1%)
Safety Analysis Population Yes	3 (100%)	3 (100%)	3 (100%)	13 (100%)	22 (100%)
Response Evaluated Analysis Population Yes	3 (100%)	3 (100%)	3 (100%)	13 (100%)	22 (100%)
Alvocidib and 7+3 Induction Yes	3 (100%)	3 (100%)	3 (100%)	13 (100%)	22 (100%)

[[]a] Number of weeks from the first dose of alvocidib to withdrawal from study

Source: Data Extract ddmmmyy; SAS (v9.4) ddmmmyy at hh:mm

Statistical Analysis Plan Protocol TPI-ALV-201

Tolero Pharmaceuticals ALV-101	ticals ALV-101	Table X.X Patient Disposition (Intent-to-Treat Population)	X.X sposition t Population)				Page 2 of 327
		Alvocidib 20/30 mg/m² (N=3)	Alvocidib 30/40 mg/m² (N=3)	Alvocidib 30/50 mg/m² (N=3)	Alvocidib 30/60 mg/m² (N=13)	Study Total (N=22)	
	Alvocidib and 5+2 Reinduction Yes No	3 (100%)	1 (33.3%) 2 (66.7%)	3 (100%)	1 (7.7%) 12 (92.3%)	2 (9.1%) 20 (90.9%)	
	HiDAC Consolidation Cycles 0 1 2 3 4	1 (33.3%) 1 (33.3%) 0 1 (33.3%)	2 (66.7%) 0 0 0 0 1 (33.3%)	1 (33.3%) 0 1 (33.3%) 1 (33.3%) 0 1 (33.3%)	9 (69.2%) 3 (23.1%) 1 (7.7%) 0	13 (59.1%) 4 (18.2%) 2 (9.1%) 2 (9.1%) 1 (4.5%)	
	Weeks on Study ^[a] Mean (S.D.) Median Min, Max	19.7 (13.8) 17.7 7.0, 34.4	15.0 (11.0) 9.4 7.9, 27.6	15.0 (8.1) 14.4 7.3, 23.4	8.1 (3.6) 9.0 3.9, 12.3	13.6 (9.1) 10.0 3.9, 34.4	
	Primary Reason Patient was Withdrawn from the Study Completed the Study Death Relapsed Disease (following remission) Lack of Efficacy (failure to achieve remission) Unknown Missing	2 (66.7%) 0 0 0 0 1 (33.3%)	2 (66.7%) 0 0 1 (33.3%) 0	1 (33.3%) 0 1 (33.3%) 1 (33.3%) 0 0	2 (15.4%) 1 (7.7%) 1 (7.7%) 1 (7.7%) 0 8 (61.5%)	7 (31.8%) 1 (4.5%) 2 (9.1%) 3 (13.6%) 1 (4.5%) 8 (36.4%)	

[a] Number of weeks from the first dose of alvocidib to withdrawal from study

Source: Data Extract ddmmmyy; SAS (v9.4) ddmmmyy at hh:mm

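### Neutrophil and platelet recovery times are censored at the last contact of any kind instead of the last blood count, so Kaplan-Meier recovery can be lowered by follow-up time in which recovery could not be seen.

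*SAP*

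**What the plan says.** SAP 7.10.5 measures time to neutrophil recovery from first dose to the first day on which the ANC is at least 1x10⁹/L for 14 consecutive days. SAP 7.10.6 does the same for platelets at 100x10⁹/L. Each section gives two censoring rules, one for loss to follow-up and one for database lock, with the same censoring date in both. A patient still below threshold "will have his time to neutrophil recovery censored on the date of his last assessment of any type", or for platelets "will have his time to platelet recovery censored on the date of his last assessment of any type". Kaplan-Meier percentages are then reported "at select milestone times (e.g., 42, 49 and 56 days") for neutrophils and "at select milestone times (e.g., 49, 56 and 63 days") for platelets, with quartile times and 95% confidence intervals.

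The other time-to-event endpoints are treated differently. For patients lost to follow-up or event-free at database lock, SAP 7.8.2, 7.8.4 and 7.8.5 censor PFS, RFS and CR duration at the last response assessment. Only overall survival (SAP 7.8.3) shares the any-type wording.

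On contacts, Protocol 5.2.4 requires hematology about weekly after induction chemotherapy, and Protocol 5.5 repeats it at End of Study. Under Protocol 5.6, whose heading calls these contacts assessments, the 30-day safety evaluation covers adverse events and medications only. After that, "all study patients will be attempted to be contacted by phone, if possible, every 6 months", to record death, transplant, relapse or continued remission. Neither contact includes a count.

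**The concern.** A Kaplan-Meier risk set should hold a patient only while the event could be observed. Recovery can be observed only on a count. If the last count was low and the last contact came later, the interval between them carries no information about recovery, but the stated rule treats it as follow-up without recovery. The any-type date suits overall survival, because any contact shows that the patient is alive. It does not suit an endpoint that needs a laboratory value.

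Both recovery times are listed safety endpoints in SAP Table 1. The late milestones lie around the 50- and 60-day cytopenia thresholds in the DLT definition (Protocol 4.4.3), so readers are likely to use these figures to judge prolonged cytopenia by dose. The Appendix 2 template shows dose groups of 3, 3, 3 and 13 patients, where one patient counts heavily.

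**Working it through.** The documents give no recovery percentage that rests on this rule, so there is no planned figure to reproduce. The check compares two rules on the same data: (A) censor at the last contact of any type, and (B) censor at the last count.

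**Direction.** The Kaplan-Meier estimate multiplies terms 1 − d/n over the recovery days, where d is the number recovering and n the number at risk. Going from B to A moves the censoring dates of unrecovered patients later. No d changes, and each n stays the same or grows. Every term is therefore equal or larger, so estimated recovery is equal or lower and quartile times are equal or later. This holds on any data set.

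**Three-patient cohort (hypothetical).** Two patients recover on Days 35 and 45. The third has a low last count on Day 40 and a phone contact on Day 70.
- Rule A: after Day 35, 1 − 1/3 = 2/3 are unrecovered. On Day 45 two are at risk, so 2/3 × (1 − 1/2) = 1/3. Recovery at Day 49 is 67%, and the upper quartile is not reached.
- Rule B: the third patient leaves the risk set at Day 40. On Day 45 one is at risk, so 2/3 × (1 − 1/1) = 0. Recovery at Day 49 is 100%, and the upper quartile is Day 45.

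**Larger groups.** Suppose k of N patients have their last count before any recovery is seen, and a non-count contact after the milestone. If F is the recovery proportion among the rest, B gives F and A gives F × (1 − k/N). F and k are assumed. N is the template total (22) or the planned maximum in Protocol 11.2 (40). With F = 80%:

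| k | N = 22 | N = 40 |
|---|---|---|
| 1 | 76.4% | 78.0% |
| 3 | 69.1% | 74.0% |
| 5 | 61.8% | 70.0% |

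**Simulation.** There were 1,500 trials per setting, with lognormal recovery, log-SD 0.28 and a last count on Day 28 for k patients. The median was 33 or 40 days; 33 is the median in Protocol 2.6.2.2, for a lower ANC threshold of 0.5x10⁹/L. With N = 22, k = 3 and median 33, recovery at Days 42/49/56 is 73.4%/83.2%/87.6% under A, 80.6%/92.1%/97.2% under B, and 80.7%/92.1%/97.1% in truth. Over k = 1, 3 and 5, both N and both medians, A is lower by about 1 to 18 points. Every leaver is given a contact after the milestones, and leaving is unrelated to recovery.

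**What the template adds.** The shortest times on study in the four dose groups are 7.0, 7.9, 7.3 and 3.9 weeks, or about Days 49, 55, 51 and 27. Assume that exits at Days 49, 51 and 55 among 14 patients (22 less the 8 with no withdrawal reason) were the last counts, and that a contact followed each milestone. The expected shift at day m is the sum of [F(m) − F(exit day)]/14. With lognormal recovery, median 33 to 40 days and log-SD 0.3, that is 0.7 to 1.5 points at Day 56 and 1.2 to 2.9 at Day 63. Whether those patients had already recovered is not shown.

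**The case against.** The strongest reply is that the rule bites only if three things coincide: the patient left unrecovered, no later count was taken, and a non-count contact followed a later recovery day in the same group. Much in the documents makes that uncommon. Counts are weekly after chemotherapy and repeated at End of Study. After one induction ending on Day 11, the 30-day safety evaluation falls on Day 41, before every milestone. SAP 7.8.3 limits follow-up to 30 days after the end-of-study visit for patients enrolled before Amendment 6 who did not reconsent, and the template's 22 patients enrolled under Amendments 2 to 4. This stands, and it limits the size. It does not remove the effect: a contact 30 days after an end-of-study visit on Days 27 to 55 falls on Days 57 to 85, beyond the last neutrophil milestone and often beyond Day 63.

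It also stands that leaving may be informative. Withdrawal reasons in the template include death, relapse and lack of efficacy. Refractory patients are less likely to recover counts, so censoring them at the last count can overstate recovery. That argues for adding a rule for these events. It does not justify counting unmeasured time as non-recovery.

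A reader might infer that the rule distorts the MTD. The documents do not support that: DLTs have their own Day 50 and Day 60 cytopenia criteria, escalation uses DLT counts, and SAP Table 3 lists no recovery table. A reader might also take the template's early exits as affected patients. The template shows time to withdrawal only, without recovery status, last count or later contact.

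**Conclusion.** The censoring date in SAP 7.10.5 and 7.10.6 is wrong as written. No other section restricts it to blood counts, and the SAP ties censoring to the relevant assessment for PFS, RFS and CR duration. The direction relative to last-count censoring is certain. The size is not. The number affected cannot be derived from the documents and is probably small, although one patient in a cohort of three can move a milestone figure from 100% to 67%.

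The simulated shortfalls should not be read as an estimate for this trial. They rest on assumed numbers of leavers, a contact after each milestone and exit unrelated to recovery. Nor does last-count censoring necessarily give the true recovery rate; it does so only if leaving is non-informative. The estimates are descriptive, and no dose decision rests on them. The change should still be made, because the correction is easy.

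**What to change.** In SAP 7.10.5, censor at the date of the last ANC; in SAP 7.10.6, at the date of the last platelet count. Apply this to both loss to follow-up and database lock, and keep the any-type date for overall survival only.

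In the same sections, state how death, refractory disease and new AML therapy before recovery are handled. One option is to treat them as competing events and report cumulative incidence of recovery.

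The cost is two changed phrases, one changed date variable and a short added rule, with no new data. The downside is more patients censored before the late milestones, and so wider intervals there.

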7.10.6. Platelet Recovery

Time to platelet recovery is defined for all patients and is measured from the date of first dose (Day 1) until the first day the platelet count is $\geq 100 \times 10^9 / L$ for 14 consecutive days. It is assumed that the platelet count remains above the threshold value of $100 \times 10^9 / L$ unless there is evidence that it did not. Therefore, a patient with platelet $\geq 100 \times 10^9 / L$ on Day 60 and without another assessment for >14 days will have a time to platelet recovery of 60 days.

Rules for censoring time to platelet recovery are:

- A patient with platelet count <100x10⁹/L as of the date he is lost to follow-up will
 have his time to platelet recovery censored on the date of his last assessment of
 any type
- A patient with platelet count <100x10⁹/L as of the database lock will have his time to platelet recovery censored on the date of his last assessment of any type

Summary statistics will include the number and percentage of censored times to platelet recovery, quartile times to platelet recovery, 95% CIs for the quartile times to platelet recovery, and KM "survival" percentages with 95% CIs at select milestone times (e.g., 49, 56 and 63 days).

7.10.7. Concomitant Medication Use

Optionally, depending on the perceived relevance, concomitant medications will mapped to terminology in the WHO DDE and then summarized within and across

alvocidib dose levels by usage rates for each level-1 ATC term and preferred (i.e., standardized) drug name.

8. Adverse Event and Medication Coding Dictionaries

The MedDRA and WHO DD versions (editions) that will be used to standardize medical terminology are not known at this time, but both will be recent editions published within 2 years before the date the first patient is enrolled into the study and the versions used will be documented in the clinical study report.

9. Summary Tables

Suggested titles for summary tables to be included in the clinical study report are shown in Table 3. The actual table titles may be altered as needed for stylistic consistency and to support text in the clinical study report. In addition, some tables listed below may be combined under a single title. A blueprint for the general format of these tables is presented in Appendix 2.

 Table 3.
 Planned Summary Tables

	Pati	ient Popu	lation
Summary Table [comments]	ITT	Safety	Per- Protocol
Patient Disposition	X		
Screening and Demographic Information	X	X	X
AML History	X	X	X
Genetic Mutations	X	X	X
Medical History	X	X	X
Pre-Existing Medical Conditions	X	X	X
Relevant Prestudy Medications	X	X	X
Study Drug Exposure	X	X	X
Complete Remission Rates – Independent			
Hematologists Review [repeat as needed for	X		X
subgroup analyses]			
Complete Remission Rates – Local Investigator	X		X
Review [repeat as needed for subgroup analyses]	Λ		77
Combined CR and Combined Remission Rates –			
Independent Hematologists Review [repeat as needed	X		X
for subgroup analyses]			
Combined CR and Combined Remission Rates –			
Local Investigator Review [repeat as needed for	X		X
subgroup analyses]			
Progression-Free Survival [repeat as needed for	X		X
subgroup analyses]	2 2		2.5
Progression-Free Survival Censoring at Transplant	X		X
[repeat as needed for subgroup analyses]	2.2		
Overall Survival [repeat as needed for subgroup	X		X
analyses]	4.4		

	Pati	ent Popu	lation
Summary Table [comments]	ITT	Safety	Per- Protocol
Relapse-Free Survival Following CR [repeat as needed for subgroup analyses]	X		X
Relapse-Free Survival Following CR Censoring at Transplant [repeat as needed for subgroup analyses]	X		X
Relapse-Free Survival Following Combined CR [repeat as needed for subgroup analyses]	X		X
Relapse-Free Survival Following Combined CR Censoring at Transplant [repeat as needed for subgroup analyses]	X		X
Relapse-Free Survival Following Combined Remission [repeat as needed for subgroup analyses]	X		X
Relapse-Free Survival Following Combined Remission Censoring at Transplant [repeat as needed for subgroup analyses]	X		X
Complete Remission Duration [repeat as needed for subgroup analyses]	X		X
Complete Remission Duration Censoring at Transplant [repeat as needed for subgroup analyses]	X		X
Combined Complete Remission Duration [repeat as needed for subgroup analyses]	X		X
Combined Complete Remission Duration Censoring at Transplant [repeat as needed for subgroup analyses]	X		X
Combined Remission Duration [repeat as needed for subgroup analyses]	X		X
Combined Remission Duration Censoring at Transplant [repeat as needed for subgroup analyses]	X		X
Stem Cell Transplant Rates	X		X
ECOG Performance Status Shift Table	X	3.7	X
30- and 60-Day Mortality Numbers of Patients with Adverse Events		X	
Treatment-Emergent Adverse Events: Incidence		Λ	
Rates by MedDRA System Organ Class		X	
Treatment-Emergent Adverse Events: Incidence		V	
Rates by MedDRA Preferred Term		X	
Treatment-Emergent Adverse Events Judged Related to Study Drug: Incidence Rates by MedDRA System Organ Class		X	
Treatment-Emergent Adverse Events Judged Related to Study Drug: Incidence Rates by MedDRA Preferred Term		X	

	Pati	ent Popul	lation
Summary Table [comments]	ITT	Safety	Per- Protocol
Treatment-Emergent Adverse Events in the Standardized MedDRA Query for Tumor Lysis Syndrome: Incidence Rates by MedDRA Preferred Term		X	
Treatment-Emergent Adverse Events in the Standardized MedDRA Query for Tumor Lysis Syndrome Judged Related to Study Drug: Incidence Rates by MedDRA Preferred Term		X	
Serious Adverse Events: Incidence Rates by MedDRA System Organ Class		X	
Serious Adverse Events: Incidence Rates by MedDRA Preferred Term		X	
Serious Adverse Events Judged Related to Study Drug: Incidence Rates by MedDRA System Organ Class		X	
Serious Adverse Events Judged Related to Study Drug: Incidence Rates by MedDRA Preferred Term		X	
Treatment-Emergent Adverse Events Leading to a Delay in the Administration of Study Drug: Incidence Rates by MedDRA Preferred Term		X	
Treatment-Emergent Adverse Events Leading to a Reduction in the Protocol-Specified Dose of Study Drug: Incidence Rates by MedDRA Preferred Term		X	

Appendix 1. Criteria for Grading Severity of Clinical Tumor Lysis Syndrome

	Grade 1	Grade 2	Grade 3	Grade 4	Grade 5
Renal	Creatinine ≤1.5 x ULN	Creatinine >1.5-3.0 x ULN	Creatinine >3.0-6.0 x ULN	Creatinine >6.0 x ULN	Death
Cardiac Arrhythmia	Intervention not indicated	Non-urgent medical intervention indicated	Symptomatic and incompletely controlled medically or controlled with device (e.g., defibrillator)	Life-threatening (e.g., arrhythmia associated with CHF, hypotension, syncope, shock)	Death
Seizure	I	One brief generalized seizure; seizure(s) well controlled by anticonvulsants or infrequent focal motor seizures not interfering with activities of daily living	Seizure in which consciousness is altered; poorly controlled seizure disorder; with breakthrough generalized seizures despite medical intervention	Seizures of any kind which are prolonged, repetitive or difficult to control (e.g., status epilepticus, intractable epilepsy)	Death

Clinical TLS requires one or more clinical manifestations (renal, cardiac, neuro) along with criteria for laboratory TLS Maximal clinical manifestation defines the severity grade ULN = upper limit of normal; 114.4 and 105.6 µmol/L will be used for males and females, respectively, if ULN is not available for an institution

Statistical Analysis Plan Protocol TPI-ALV-201

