2.6.2.1 Summary of Safety in NCI-7845 (J-0669) FLAM in Newly-diagnosed Poor-risk AML

All-grade Tumor Lysis Syndrome was observed in 19/45 (42%), with one patient expiring due to disseminated intravascular coagulation (DIC) and multiorgan failure. Treatment-related mortality (TRM) at 30 days was observed in 2 patients (4%), with one patient each with TLS/DIC/multiorgan failure and fungal infection. TRM at 60 days was observed in 2 additional patients (4%), both died from sepsis. Adverse events Grade ≥ 3 included: 11% GI mucositis, 11% reversible SV arrhythmia with sepsis, 7% sepsis, 4% oral mucositis, and 4% diarrhea.

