4.2.2 Inclusion Criteria

To be eligible for participation in the study, patients must meet all of the following inclusion criteria:

1. Be between the ages of ≥ 18 and ≤ 65 years
2. Have an established, pathologically confirmed diagnoses of AML by World Health Organization (WHO) criteria with $\geq 20\%$ bone marrow blasts based on histology or flow cytometry
3. Be newly diagnosed and previously untreated
4. Have an Eastern Cooperative Oncology Group (ECOG) performance status (PS) ≤ 2
5. Have a serum creatinine level ≤ 1.8 mg/dL
6. Have an alanine aminotransferase (ALT) and aspartate aminotransferase (AST) level ≤ 5 times upper limit of normal (ULN)

7. Have a total bilirubin level ≤ 2.0 mg/dL (unless secondary to Gilbert syndrome, hemolysis, or leukemia)
8. Have a left ventricular ejection fraction (LVEF) $>45\%$ by echocardiogram (ECHO) or multigated acquisition (MUGA) scan
9. Be nonfertile or agree to use an adequate method of contraception. Sexually active patients and their partners must use an effective method of contraception associated with a low failure rate prior to study entry, for the duration of study participation, and for at least 6 months after the last dose of study drug (see [Section 4.5.3](#)).
10. Be able to comply with the requirements of the entire study.
11. Provide written informed consent prior to any study related procedure. (In the event that the patient is re-screened for study participation or a protocol amendment alters the care of an ongoing patient, a new informed consent form must be signed.)

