7.10.3. Classification of Tumor Lysis Syndrome

Cairo-Bishop definitions for laboratory TLS and clinical TLS will be used to diagnose and grade TLS.¹⁴ Patients are classified as experiencing laboratory TLS if they have any two or more serum values of uric acid, potassium, phosphorus and/or calcium shown in Table 2 within 3 days before or 7 days after the initiation of study drug.

Table 2. Cairo-Bishop Definition of Laboratory Tumor Lysis Syndrome

Laboratory Parameter	Criteria
Uric Acid	≥476 µmol/L or 25% increase from baseline
Potassium	≥6.0 mmol/L or 25% increase from baseline
Phosphorus	≥1.45 mmol/L or 25% increase from baseline
Calcium	≤1.75 mmol/L or 25% decrease from baseline

Diagnosis of clinical TLS requires the presence of laboratory TLS and elevated serum creatinine levels, cardiac arrhythmia and/or seizures. Criteria for grading the severity of clinical TLS are presented in Appendix 1.

The numbers of patients experiencing laboratory TLS and the various severities of clinical TLS will be summarized within and across alvocidib dose levels.

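### SAP Appendix 1 gives renal Grade 1 no lower bound, SAP 7.10.3 asks for an undefined elevated creatinine, and neither uses the pre-dose value, so Grade 1 clinical tumor lysis syndrome is not fixed

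*SAP*

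**What the plan says.** SAP 7.10.3 separates diagnosis from grading. On diagnosis it says: "Diagnosis of clinical TLS requires the presence of laboratory TLS and elevated serum creatinine levels, cardiac arrhythmia and/or seizures". The next sentence points to the grid: "Criteria for grading the severity of clinical TLS are presented in Appendix 1". No cut-off for *elevated* is given there or elsewhere.

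In SAP Appendix 1 the renal row starts with "Creatinine ≤1.5 x ULN" for Grade 1 and continues with "Creatinine >1.5-3.0 x ULN" for Grade 2. There is no Grade 0 column. The footnote says "Clinical TLS requires one or more clinical manifestations (renal, cardiac, neuro) along with criteria for laboratory TLS", without saying what counts as a renal manifestation, and lets the worst manifestation set the grade. It supplies fallback ULNs of 114.4 µmol/L (men) and 105.6 µmol/L (women) for institutions without their own.

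On reporting, SAP 7.10.3 states: "The numbers of patients experiencing laboratory TLS and the various severities of clinical TLS will be summarized within and across alvocidib dose levels". SAP Table 3 plans two tables by maximum grade, one for Cycle 1 and one for the whole study. Presence and severity of TLS is a named safety endpoint in SAP 4.1.

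Protocol 4.2.2 item 5 ("Have a serum creatinine level") admits patients up to 1.8 mg/dL.

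**The concern.** The grid and the diagnostic rule disagree about a patient with laboratory TLS and a normal creatinine: the Grade 1 cell includes that patient and the diagnostic sentence does not. Because *elevated* has no cut-off, two programmers could follow the same SAP and report different Grade 1 counts.

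The pre-dose value is a second problem. Each laboratory TLS criterion in SAP Table 2 offers a change-from-baseline alternative, but the renal criterion has none. Renal impairment present at entry can therefore be reported as a TLS manifestation.

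The third problem is timing. Laboratory TLS is tied to a window from 3 days before to 7 days after the start of study drug. Arrhythmia and seizure have no window, and one table covers the whole study. Protocol 2.6.2.1 shows why this matters: in an earlier alvocidib study with 42% all-grade TLS, the Grade 3 or higher events included "11% reversible SV arrhythmia with sepsis". A similar arrhythmia weeks later, in a patient who had laboratory TLS, would meet the text of 7.10.3.

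At stake is whether the TLS tables separate a biochemical finding from organ involvement at each dose.

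**Working it through.** The plan states no figure to reproduce, so the check applies the rule case by case.

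**1. The rule by creatinine level.** Take a patient with laboratory TLS, no arrhythmia and no seizure. *Elevated* is tried at two cut-offs, because the SAP gives none.

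| Creatinine (x ULN) | Appendix 1 cells alone | 7.10.3 first, elevated = >1.0 | 7.10.3 first, elevated = >1.5 |
|---|---|---|---|
| 0.7, 1.0 | Grade 1 | not clinical TLS | not clinical TLS |
| 1.01, 1.2, 1.5 | Grade 1 | Grade 1 | not clinical TLS |
| 1.6, 3.0 | Grade 2 | Grade 2 | Grade 2 |
| 3.1 | Grade 3 | Grade 3 | Grade 3 |
| 6.1 | Grade 4 | Grade 4 | Grade 4 |

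Only the first two rows differ. With 7.10.3 applied, the first row is settled and the second is not. At a cut-off of >1.5 x ULN the renal Grade 1 cell can never be filled, which makes that reading unlikely but not excluded.

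**2. Entry creatinine against ULN.** The documents give no conversion factor. The fallback ULNs imply 88.0 µmol/L per mg/dL, since 1.3 x 88.0 = 114.4 and 1.2 x 88.0 = 105.6. A value of 88.4 is also tried.

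- At 88.0: 1.8 mg/dL = 158.4 µmol/L; 158.4/114.4 = 1.385 x ULN (men) and 158.4/105.6 = 1.500 x ULN (women).
- At 88.4: 1.8 mg/dL = 159.12 µmol/L; 159.12/114.4 = 1.391 (men) and 159.12/105.6 = 1.507 (women).

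So a man entering above about 1.3 and up to 1.8 mg/dL, or a woman above about 1.2 and up to 1.8 mg/dL, is eligible and already above the fallback ULN. If *elevated* means above ULN, such a patient needs only laboratory TLS to be counted as clinical TLS, with no renal change.

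**3. Weight of one patient.** Protocol Table 3 plans 3 to 6 patients per cohort. The SAP Appendix 2 template shows dose groups of 3, 3, 3 and 13. One reclassified patient moves the rate by 1/3 = 33.3, 1/6 = 16.7 or 1/13 = 7.7 percentage points.

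**4. Link to dose decisions.** Protocol 4.4.3 defines DLTs by CTCAE 4.03, with its own TLS and creatinine rules. It does not use Appendix 1.

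**The case against.** The strongest reply is that the SAP already puts diagnosis before grading. A patient with laboratory TLS, normal creatinine and no other manifestation is never diagnosed, so never graded, and laboratory TLS is counted as well. This stands. A reader of the grid alone might infer that every laboratory TLS case is reported as clinical TLS. The documents do not support that, because both 7.10.3 and the Appendix 1 footnote require a clinical manifestation.

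A reader might also infer that a woman at the entry limit is Grade 2 before treatment. That depends on the conversion factor. At the 88.0 implied by the fallback ULNs she is at exactly 1.5 x ULN, which is Grade 1. Protocol 10.4 also has sites keep normal ranges on file, so the fallback may rarely apply.

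A further reply is that the SAP adopts a published definition, so adding a baseline condition alters it. That is a fair cost, to be disclosed. Finally, SAP 7.10.2 summarizes related TLS-query events and 7.10.4 plans CTCAE shift tables. These help a reader to spot pre-existing elevation or another cause, but they do not correct the two graded TLS tables.

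**Conclusion.** The two SAP passages conflict, and the conflict matters at the lower end of the scale. Applying 7.10.3 first removes normal-creatinine patients. It leaves open the Grade 1 count between 1.0 and 1.5 x ULN, the handling of patients already above ULN at entry, and the timing of arrhythmia and seizure.

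The entry-creatinine consequence assumes that *elevated* means above ULN; the mg/dL figures also assume the fallback ULNs. The number of patients affected cannot be computed. The documents give no laboratory-only TLS rate, and the TLS rates quoted from earlier studies in Protocol 2.6.2 are not said to follow this definition, so no overall overstatement factor can be supported.

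The impact is confined to descriptive TLS tables, mainly the Grade 1 line. It concerns a named safety endpoint in cohorts as small as 3, so it is worth correcting before database lock. It does not touch DLT or MTD decisions.

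**What to change.** Reconcile SAP Appendix 1 with 7.10.3, for analysis purposes only:

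- Restate renal Grade 1 as >1.0 to 1.5 x ULN, and use the same >1.0 x ULN cut-off for *elevated* in 7.10.3.
- Count a renal manifestation of any grade only if creatinine exceeds the patient's pre-dose baseline, as the SAP already defines baseline.
- Show laboratory-only TLS as its own row in both TLS tables.
- Count an arrhythmia or seizure only if it falls in the window that 7.10.3 already sets for laboratory TLS. State whether that window restarts with each cycle, because the whole-study table depends on it.

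The cost is SAP wording and a few lines of programming. Pre-dose creatinine is collected under Protocol 5.1.2 and 5.2.1.2, and event dates under 8.4. The result departs slightly from the published grid and should be footnoted. One limit remains: creatinine is drawn repeatedly during alvocidib treatment, so any rise above baseline is a weak filter. The documents give no figure for a minimum rise, and none is proposed here.
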